1.1 Disease-Free Survival

Disease-Free survival (DFS) is defined as the time from date of randomization to documentation of 1st disease recurrence or death due to any cause, whichever occurs first. Patients who fail to return for evaluation after beginning therapy will be censored for DFS on the last day of therapy. Patients who are lost to follow-up after completing therapy will be censored for DFS on the date they were last confirmed to be disease free.

2.0 ACCRUAL

It is anticipated that 6 trials world-wide will contribute patients. The specific trials, and accrual goals (for stage III colon cancer patients) are indicated in the table below.

	TOSCA	SCOT	Alliance/ SWOG	GERCOR/ PRODIGE	HORG	ACHIEVE
Expected accrual	2350	4400	2500	2000	1000	1500
Accrual period	6/2007 – 3/2013	3/2008 – 11/2013	6/2010 – 6/2015	5/2009 – 6/2013	10/2010 – 12/2014	8/2012- 8/2014

3.0 POWER CONSIDERATIONS

The 3 year DFS rate for patients with stage III disease has been highly consistent over the last decade, at 72% from both MOSAIC and N0147. A sample size of 10,500 patients, based on an expected accrual duration of 4.5 years, 1.5 years minimum follow-up, and an expected 3 year DFS rate in the control (6 month) group of 72%, is expected to provide 3390 DFS events required to provide 90% power to declare non-inferiority of the 3 month arm when the true hazard ratio between arms is 1.0. This design has a type one error rate of 0.025 if the true hazard ratio between arms is 1.12. This hazard rate, in an exponential survival model, corresponds to a decrease in the 3 year DFS rate on the 3 month arm to 69.2%. In this design the critical driver of the analysis timing is the number of DFS events, as the precise accrual and follow-up patterns will differ by study and are impossible to precisely anticipate.

4.0 ANALYSIS PLAN**4.1 Primary efficacy analysis**

The primary IDEA efficacy analysis will consist of estimating the hazard ratio for DFS comparing 3 versus 6 months of therapy using a Cox proportional hazards regression model.

The Cox regression will be stratified for the initial study that each participant was enrolled to. Individual IDEA trials may also have study specific sub-questions, however to protect the integrity of each individual trial, the study-specific sub-question randomization will be pooled for the IDEA analysis. The primary analyses will be modified intention to treat, including patients in their randomized arm regardless of the actual treatment or duration of treatment received, with only patients who receive no therapy whatsoever excluded from the analysis. This is the result of the potential bias of a per-protocol analysis, which may be typically considered for a non-inferiority trial, in that patients on the 6 month arm who complete 3 or fewer months of therapy may be a biased sub-group to include with patients randomized to the 3 month arm as would be done in a per-protocol analysis.

The timing of the analysis will be event driven. Given that this is a non-inferiority trial, and there is no expectation of superior results for the reduced duration therapy, an interim analysis to conclude non-inferiority will not be conducted. A single interim analyses to reject H1 and conclude inferiority of 3 months of therapy is planned, at 50% of the protocol specified pooled number of events. Because this interim will occur after most (if not all) trials have closed to accrual, we will use the Lan-Demets implementation of the O'Brien-Fleming stopping boundaries for futility to be able to declare non-inferiority. The significance values to be used at each analysis (interim and final), are outlined in [Section 4.2](#).

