4.1.1 Test statistic

The formal test statistic for the analysis will be a Z-statistic generated using the log-hazard ratio for the covariate of randomization to the 3 month or 6 month arm from a univariate Cox regression model, stratified by trial. If $\delta = -\ln(\text{HR})$, and $\delta_0 = -\ln(1.12)$, then $Z = (\delta_0 - \delta) / \text{SE}(\delta)$.

4.1.2 Critical values.

Based on two analyses occurring at 50% and 100% of expected events, the critical Z-values to reject the alternative hypothesis (and thus conclude that non-inferiority is not attained) are $Z < -0.254$ and $Z < -1.947$. This corresponds, approximately, to hazard ratios comparing the 3 to 6 month arm of > 1.106 and 1.047 respectively for the 2 analyses to reject the alternative hypothesis of non-inferiority. Under the null hypothesis of inferiority (true HR = 1.12), the trial will terminate for futility (inability to conclude non-inferiority) at the 50% of events mark with approximately 60% probability. The interim analyses will be conducted by an independent statistician and presented to an IDEA-specific DSMB. As it will be difficult to precisely coordinate the timing of the interim and final analyses to a specific number of events, the specific cut-off values for terminating the trial at the interim analyses will be based on the O'Brien-Fleming family boundaries at the actual number of events observed.

4.2 Assessing treatment effect heterogeneity:

At both the interim and final analyses, individual trial HRs with confidence intervals will be plotted using a forest plot. Potential heterogeneity in treatment effects will be assessed by the procedures specified in Section 4.2.1 and 4.2.2. If heterogeneity in the in treatment effect across studies is detected, subgroup analysis (excluding outlier trial(s)) and meta-regression analysis will be conducted to assess the robustness of the primary efficacy results and investigate the trial characteristics (trial design, enrolling country, etc.) which may contribute to the heterogeneity.

4.2.1 Primary assessment by likelihood ratio test:

Primary assessment by likelihood ratio test: Two stratified (by study) Cox models will be fit to the data, 1) Full model: with both treatment assignment and trial-specific indicator (dummy variables) as predictors; and 2) Reduced model: with only treatment assignment as

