5.2 Analysis plans for OS

Analysis plans for OS will parallel those outlined for DFS, including the hypotheses to be tested, the error rates spent for each comparison, and the number of events required prior to analysis. As the event rates for overall survival at 5 years and for DFS at 3 years are very similar in the setting of adjuvant colon cancer the data for OS will be mature after the data for DFS. We expect the data for OS to be mature between 4 - 6 years following the close of accrual.

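### IDEA interim (Appendix VI): Section 4.1 says a crossing concludes inferiority of 3 months, but the futility boundary in Section 4.1.2 shows only that non-inferiority cannot be concluded

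*Combined protocol and SAP*

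**What the plan says.** Appendix VI sets out the pooled IDEA comparison of 3 against 6 months of therapy.

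- Section 3.0 fixes the size: the sample "is expected to provide 3390 DFS events required to provide 90% power to declare non-inferiority of the 3 month arm". That power refers to equal hazards, a hazard ratio (HR) of 1.0. The section also fixes the margin: "This design has a type one error rate of 0.025 if the true hazard ratio between arms is 1.12".
- Section 4.1 states the purpose of the one interim look: "A single interim analyses to reject H1 and conclude inferiority of 3 months of therapy is planned". The look is timed by events, "at 50% of the protocol specified pooled number of events". The section then names the boundary as the "Lan-Demets implementation of the O'Brien-Fleming stopping boundaries for futility to be able to declare non-inferiority".
- Section 4.1.2 gives critical values of -0.254 and -1.947 and translates them into "hazard ratios comparing the 3 to 6 month arm of > 1.106 and 1.047 respectively". It describes what a crossing means: "Under the null hypothesis of inferiority (true HR = 1.12), the trial will terminate for futility (inability to conclude non-inferiority"), with a probability of about 60% at the 50% look. It also says that rejecting the alternative means non-inferiority is not attained.

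**The concern.** Failing to show non-inferiority and showing inferiority are different findings. Section 4.1 assigns the second to an interim crossing and Section 4.1.2 assigns the first. Section 4.1.2 also ties inferiority to HR = 1.12, yet the interim cut-off of 1.106 is below that value, so an estimate just over the cut-off does not even reach the margin, let alone exclude everything below it.

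What is at stake is the message a crossing would carry. An independent statistician and an IDEA-specific DSMB apply this text. Under Section 4.1 they could conclude that the shorter regimen is inferior. Under Section 4.1.2 the same data say only that the trial cannot establish non-inferiority. The pre-specified meaning should be single and should match what the boundary can support.

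**Working it through.** **Inputs.** Total events 3,390, margin 1.12 and type I error 0.025 (Section 3.0); interim at 50%, so 1,695 events (Section 4.1); critical values -0.254 and -1.947 (Section 4.1.2). Allocation of 1:1 is an assumption; the appendix gives no ratio, but the stated cut-offs reproduce with it.

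**Direction.** With the definitions printed in Section 4.1.1, Z = (δ0 - δ)/SE equals ln(HR/1.12)/SE, so Z below -0.254 would mean an HR *below* 1.106. The HR form of the rule and the 60% figure show that the intended stop is for an HR *above* 1.106. That direction is used here.

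**Reproducing the plan.** SE(ln HR) = 2/√events.

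- Interim: 2/√1695 = 0.04858. Final: 2/√3390 = 0.03435.
- Interim cut-off: 1.12 × exp(-0.254 × 0.04858) = 1.1063 (stated 1.106).
- Final cut-off: 1.12 × exp(-1.947 × 0.03435) = 1.0475 (stated 1.047).
- Stopping probability at true HR 1.12: 1 - Φ(-0.254) = 0.600 (stated about 60%).
- Type I error at true HR 1.12, meaning both estimates fall below their cut-offs (bivariate normal, correlation √0.5): 0.0250 (stated 0.025).
- Power at true HR 1.0: 0.906 (stated 90%).

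**What an estimate on the boundary shows.**

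- 95% CI: exp(ln 1.1063 ± 1.96 × 0.04858) = 1.006 to 1.217, which contains 1.12.
- One-sided p for HR above 1.12: 0.60.
- Against HR = 1: ln 1.1063/0.04858 = 2.08, two-sided p about 0.038.
- Observed HR needed at 1,695 events for the lower 95% limit to exceed 1.12: 1.12 × exp(1.96 × 0.04858) = 1.232.

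**How often the boundary is crossed.** P(cross) = 1 - Φ((ln 1.1063 - ln HR)/0.04858). The other columns give the chance of declaring non-inferiority at the end without and with the interim stop.

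| True HR | P(cross) | Success, no interim | Success, with interim | Difference |
|---|---|---|---|---|
| 1.00 | 0.0188 | 0.9118 | 0.9060 | 0.0058 |
| 1.05 | 0.1413 | 0.4728 | 0.4645 | 0.0083 |
| 1.10 | 0.4535 | 0.0774 | 0.0753 | 0.0021 |
| 1.12 | 0.6003 | 0.0258 | 0.0250 | 0.0008 |

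If the look falls at 45% to 55% of events with the cut-off held at 1.106, the crossing probability is 13% to 16% at HR 1.05 and 45% to 46% at HR 1.10.

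**The case against.** **The text largely corrects itself.** Section 4.1 goes on to call the boundaries futility boundaries, and the operative Section 4.1.2 says twice that a crossing means non-inferiority is not attained. This stands: the right reading is already in the plan. It does not remove the conflict, because Section 4.1 is where the purpose of the interim is stated.

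**HR = 1 is nominally excluded at the boundary.** That is true (z = 2.08), and inferiority in the sense of any HR above 1 would have nominal support. The plan does not define inferiority that way.

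**Stronger readings that a reader might infer.**

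- *The boundary is badly placed because it lies inside the margin.* The documents do not support this. The final analysis itself needs an HR below about 1.047, so a futility cut-off of 1.106 is ordinary. In the table the stop costs under one percentage point of success at each true HR. Of the crossings, only about 6% at HR 1.05 (0.0083/0.1413) and 0.5% at HR 1.10 (0.0021/0.4535) would have ended in non-inferiority. The 14% and 45% are stopping probabilities. They become wrong claims of inferiority only if the phrase in Section 4.1 is taken at its word.
- *The type I error exceeds 0.025 because follow-up continues for overall survival.* Section 4.1.2 says the trial will terminate, so the stop is binding as written and the error is 0.0250. Nothing provides for a second DFS test after a crossing. Section 5.2 carries over to overall survival "the error rates spent for each comparison, and the number of events required prior to analysis"; it does not reopen DFS. Even in that hypothetical case the error would be 0.0258, an excess of 0.0008. A non-binding rule with 1.960 at the end would be a design preference, not a correction.
- *A crossing would be published as proof of inferiority.* No section sets such a reporting rule.

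**Timing and ownership.** This trial only contributes data to IDEA, and Section 13.1 of the protocol already cites IDEA pooled results. This limits the prospective effect of a change on the DFS interim and is another reason to confine the point to wording.

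**Conclusion.** The point holds as a contradiction about what a crossing may conclude, and it is not a fault in the design. Section 4.1 attaches to the interim boundary a conclusion that the boundary cannot support under the plan's own definition of inferiority: the 95% CI at the boundary, about 1.006 to 1.217, contains 1.12. Read literally, Section 4.1 would declare inferiority in 14% of cases at a true HR of 1.05 and 45% at 1.10. The boundary location, the magnitudes of the critical values and the stated type I error of 0.025 under the binding stop need no change.

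The figures assume 1:1 allocation, the usual large-sample standard error of 2/√events, a look at 1,695 events, and the direction of the rule given by the HR cut-offs.

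**What to change.** In Appendix VI, Section 4.1, replace the statement that the interim rejects H1 and concludes inferiority with one that matches Section 4.1.2: *the interim may reject H1 and stop for futility, in which case non-inferiority cannot be concluded*. Add one sentence: *a crossing is not by itself to be reported as demonstrating inferiority by the 1.12 margin; the hazard ratio is reported with its confidence interval*. Since Section 5.2 models the overall survival plan on the DFS plan, the aligned wording should apply there too if the interim rule is carried over.

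The cost is two sentences. Events, boundaries, error rates and power are unchanged. While Section 4.1.2 is open, the direction of the Z inequalities should be reconciled with the HR cut-offs; that is a separate correction of notation.

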4.1.1 Test statistic

The formal test statistic for the analysis will be a Z-statistic generated using the log-hazard ratio for the covariate of randomization to the 3 month or 6 month arm from a univariate Cox regression model, stratified by trial. If $\delta = -\ln(\text{HR})$, and $\delta_0 = -\ln(1.12)$, then $Z = (\delta_0 - \delta) / \text{SE}(\delta)$.

4.1.2 Critical values.

Based on two analyses occurring at 50% and 100% of expected events, the critical Z-values to reject the alternative hypothesis (and thus conclude that non-inferiority is not attained) are $Z < -0.254$ and $Z < -1.947$. This corresponds, approximately, to hazard ratios comparing the 3 to 6 month arm of > 1.106 and 1.047 respectively for the 2 analyses to reject the alternative hypothesis of non-inferiority. Under the null hypothesis of inferiority (true HR = 1.12), the trial will terminate for futility (inability to conclude non-inferiority) at the 50% of events mark with approximately 60% probability. The interim analyses will be conducted by an independent statistician and presented to an IDEA-specific DSMB. As it will be difficult to precisely coordinate the timing of the interim and final analyses to a specific number of events, the specific cut-off values for terminating the trial at the interim analyses will be based on the O'Brien-Fleming family boundaries at the actual number of events observed.

4.2 Assessing treatment effect heterogeneity:

At both the interim and final analyses, individual trial HRs with confidence intervals will be plotted using a forest plot. Potential heterogeneity in treatment effects will be assessed by the procedures specified in Section 4.2.1 and 4.2.2. If heterogeneity in the in treatment effect across studies is detected, subgroup analysis (excluding outlier trial(s)) and meta-regression analysis will be conducted to assess the robustness of the primary efficacy results and investigate the trial characteristics (trial design, enrolling country, etc.) which may contribute to the heterogeneity.

4.2.1 Primary assessment by likelihood ratio test:

Primary assessment by likelihood ratio test: Two stratified (by study) Cox models will be fit to the data, 1) Full model: with both treatment assignment and trial-specific indicator (dummy variables) as predictors; and 2) Reduced model: with only treatment assignment as

the predictor. The likelihood ratio test will be used to test whether the full model significantly fits the data better than reduced model. A p-value less than 0.05 will be taken to indicate significant trial-specific heterogeneity of treatment effect. In that case, the trial specific treatment effect estimates (hazard ratios) and p-values associated with each of the trial indicator will be further examined to detect the specific heterogeneity (i.e., differences between trials).

5.0 SECONDARY ENDPOINTS AND ANALYSES.

Secondary endpoints include overall survival, toxicity, and treatment compliance with the randomized regimen. A formal statistical analysis plan will be developed prior to actual conduct of the analyses for secondary endpoints.

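### The critical Z-values for the pooled IDEA non-inferiority analysis have their inequalities reversed, contradicting the plan's own hazard-ratio limits, type I error and power.

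*Combined protocol and SAP*

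**What the plan says.** Appendix VI describes the pooled comparison of 3 with 6 months of chemotherapy, to which this trial contributes under secondary objectives 2.2.1 and 2.2.3. Section 4.1 makes the hazard ratio a 3 versus 6 month comparison, so values above 1 mean that 3 months is worse.

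- Section 4.1.1, definitions: "If $\delta = -\ln(\text{HR})$, and $\delta_0 = -\ln(1.12"), "then $Z = (\delta_0 - \delta) / \text{SE}(\delta").
- Section 4.1.2, Z scale: "the critical Z-values to reject the alternative hypothesis (and thus conclude that non-inferiority is not attained) are $Z < -0.254$ and $Z < -1.947".
- Section 4.1.2, next sentence, hazard-ratio scale: "hazard ratios comparing the 3 to 6 month arm of > 1.106 and 1.047 respectively for the 2 analyses".
- Section 4.1.2, at a true hazard ratio of 1.12: "the trial will terminate for futility (inability to conclude non-inferiority) at the 50% of events mark with approximately 60% probability".
- Section 3.0: the design "is expected to provide 3390 DFS events required to provide 90% power to declare non-inferiority of the 3 month arm" when the true hazard ratio is 1.0, with type I error 0.025 at 1.12.

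**The concern.** Two consecutive sentences in Section 4.1.2 give opposite decisions on the same data. Because Z rises with the hazard ratio, a rule that rejects non-inferiority for sufficiently negative Z rejects it when 3 months performs well.

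The Z statement is the formal one: Section 4.1.1 names Z as the formal test statistic, and the hazard ratios are offered only as approximate equivalents. They hold only at the planned event counts, while Section 4.1.2 says the interim cut-off will be reset to the events actually observed. An analyst who recalculates the boundary therefore needs the correct direction on the Z scale. Section 4.1 points to Section 4.2 for the significance values, but 4.2 deals with heterogeneity, so 4.1.2 is the only place where the boundaries are given. Section 5.2 makes the overall survival analysis parallel the disease-free survival analysis, so the error carries over.

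**Working it through.** **Inputs.** Margin 1.12, 3390 events, type I error 0.025 and 90% power (Appendix VI, Section 3.0). Looks at 50% and 100% of events, so 1695 and 3390; critical values −0.254 and −1.947 (Section 4.1.2). Assumption: 1:1 allocation, which is not stated for IDEA, so SE(ln HR) = 2/√events. This affects magnitudes but not direction.

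**1. The statistic.** With δ = −ln(HR) and δ₀ = −ln(1.12):

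Z = (δ₀ − δ)/SE = [ln(HR) − ln(1.12)]/SE = ln(HR/1.12)/SE.

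Z increases with HR.

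**2. Reproduce the plan's hazard-ratio limits.** The boundary hazard ratio is 1.12 × exp(c × SE).

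- Interim: SE = 2/√1695 = 0.04858; 1.12 × exp(−0.254 × 0.04858) = 1.1063 (plan: 1.106).
- Final: SE = 2/√3390 = 0.03435; 1.12 × exp(−1.947 × 0.03435) = 1.0475 (plan: 1.047).

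The magnitudes are right.

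**3. Direction.** Since Z rises with HR, Z < −0.254 means HR < 1.106 and Z < −1.947 means HR < 1.047. The plan's next sentence has HR above both values. An observed HR of 1.00 gives Z = −2.33 at the interim and −3.30 at the end, so the printed Z rule denies non-inferiority. An observed HR of 1.20 gives +1.42 and +2.01, so it does not.

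**4. Which sentence matches the design?** At a true HR of 1.12, P(Z > −0.254) = 0.600, the plan's figure, whereas P(Z < −0.254) = 0.400. At a true HR of 1.00 the mean of Z is −2.333 at the interim and −3.299 at the end. The printed rule then stops at the interim with probability Φ(2.333 − 0.254) = 0.981. Taken alone, ignoring the interim, the final look says not attained with probability Φ(3.299 − 1.947) = 0.912. Over both looks (bivariate normal, correlation √0.5):

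| True HR | Quantity | Plan | Z rule as printed | Inequalities reversed |
|---|---|---|---|---|
| 1.00 | Interim futility stop | not given | 0.981 | 0.019 |
| 1.00 | Non-inferiority concluded | 0.90 | 0.013 | 0.906 |
| 1.12 | Interim futility stop | about 0.60 | 0.400 | 0.600 |
| 1.12 | Non-inferiority concluded | 0.025 | 0.599 | 0.0250 |

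**5. Other readings.** Changing only the signs of the critical values, or only the order of subtraction in Z, puts the cut-offs at 1.134 and 1.197, which do not match. Reading the hazard ratio as 6 versus 3 months contradicts Sections 4.1 and 4.1.2 and gives an interim cut-off of about 1/1.106 = 0.904 on the 3 versus 6 scale. Only two repairs reproduce every stated figure: reversing the inequalities, or changing both the formula and the critical-value signs.

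**The case against.** The strongest reply is that the correct rule stands in the very next sentence, in plain hazard-ratio terms, and that the 60% figure, the type I error and the power all agree with it. Nobody reading the whole paragraph would apply the reversed rule, so the probabilities for the printed version describe something unlikely to happen. That stands as a point about consequence: the paragraph contradicts itself, and the intended rule can be recovered.

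Three further points also carry some weight.

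- Section 13.1 of the protocol already cites a reported IDEA pooled analysis, so the disease-free survival interim is probably no longer a pending decision. Overall survival may be, although Section 5.0 of the appendix requires a separate analysis plan first.
- The interim goes to an independent statistician and a dedicated monitoring board, with the boundary reset to the observed events. That is a safeguard, but it is also a reason for the direction on the Z scale to be right.
- The error does not touch this trial's primary celecoxib comparison.

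None of this makes the printed inequalities correct.

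**Conclusion.** The concern holds. The two Z inequalities in Section 4.1.2 point the wrong way relative to the plan's own statistic, hazard-ratio limits, futility probability, type I error and power. Taken literally, the rule turns a design with 90% power and 0.025 type I error into one that concludes non-inferiority with probability 0.013 when the arms are equal and 0.599 at the margin. The direction error follows from the definitions alone. The probabilities also rest on 1:1 allocation, looks at exactly 1695 and 3390 events, and the normal approximation to ln(HR). The boundary magnitudes are sound, so nothing in the design needs revisiting. A formal decision rule that contradicts itself on direction should still be corrected, because overall survival inherits it and anyone checking the reported analysis against the plan would meet the contradiction.

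**What to change.** Keep Z = (δ₀ − δ)/SE and restate the rule as follows. Reject non-inferiority if Z > −0.254 at the interim or Z > −1.947 at the final analysis; conclude non-inferiority at the final analysis if Z ≤ −1.947, which is a hazard ratio of at most about 1.047 at 3390 events. Equivalently, define Z = (δ − δ₀)/SE and reject for Z < 0.254 and Z < 1.947. Keep the provision that the interim cut-off is recalculated at the actual number of events, in the same direction. Correct the cross-reference in Section 4.1 so that it leads to 4.1.2, carry the corrected direction into the overall survival analysis plan, and record which direction was used in the pooled disease-free survival analysis already reported.

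The cost is a short wording change. No boundary magnitude, event count, patient or data item is affected. Because Appendix VI describes a plan shared by six trials, the correction should be agreed with the IDEA steering committee so that all versions match.

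### The primary test for between-trial heterogeneity in IDEA (Appendix VI, 4.2.1) adds trial dummies to a Cox model already stratified by trial, so its statistic is zero for any data

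*Combined protocol and SAP*

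**What the plan says.** Appendix VI, Section 4.2 plans a forest plot of the trial HRs at the interim and final analyses, and then formal assessment: "Potential heterogeneity in treatment effects will be assessed by the procedures specified in Section 4.2.1 and 4.2.2". If heterogeneity is found, analyses that leave out outlying trials and a meta-regression follow.

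Section 4.2.1 is headed as the primary assessment. It says "Two stratified (by study) Cox models will be fit to the data". The larger is "Full model: with both treatment assignment and trial-specific indicator (dummy variables) as predictors"; the smaller is "Reduced model: with only treatment assignment as" the predictor. Then: "The likelihood ratio test will be used to test whether the full model significantly fits the data better than reduced model". The decision rule is "A p-value less than 0.05 will be taken to indicate significant trial-specific heterogeneity of treatment effect", and in that event "the trial specific treatment effect estimates (hazard ratios) and p-values associated with each of the trial indicator will be further examined".

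No product of treatment and trial appears in the stated models. Section 4.2.2 is cited, but it is not in the supplied text. For overall survival, Section 5.2 says: "Analysis plans for OS will parallel those outlined for DFS, including the hypotheses to be tested".

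**The concern.** Two things are wrong with the stated pair of models.

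- **Redundant terms.** Stratifying by study already gives each trial its own unrestricted baseline hazard. Adding a main-effect dummy for the same trial adds nothing that the partial likelihood can see.
- **Wrong quantity.** Even without stratification, a trial main effect describes how the baseline hazard differs between trials. It does not describe how the treatment effect differs.

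The question matters because IDEA pools six trials that differ in regimen (FOLFOX or XELOX) and in design, and draws one non-inferiority conclusion against a margin of 1.12. A pooled HR under the final limit of 1.047 can average over trials on both sides of that margin. Section 4.2 makes the robustness analyses conditional on heterogeneity being detected, and 4.2.1 is its named primary detector.

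**Working it through.** **Inputs.** From Appendix VI: six trials with accrual goals 2350, 4400, 2500, 2000, 1000 and 1500, which sum to 13,750 (Section 2.0); 3,390 DFS events, margin 1.12, type I error 0.025, control 3-year DFS 72% (Section 3.0); final critical value Z = -1.947 (Section 4.1.2).

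**1. The plan's own figures.** Section 4.2.1 gives no power for the heterogeneity test, so the pooled design is reproduced instead.

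- With SE(log HR) = 2/√events, power = Φ(ln 1.12 × √3390 / 2 − 1.96) = Φ(1.34) = 0.91, against 90% stated.
- 3-year DFS at the margin: 0.72^1.12 = 69.2%, as stated.
- Final limit: exp(ln 1.12 − 1.947 × 2/√3390) = 1.0475, against 1.047 stated.

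The pooled design holds together. The problem is confined to 4.2.1.

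**2. The test as written.** For an event in patient i of trial k, the stratified partial likelihood contributes

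exp(βxᵢ + γₖ) / Σⱼ exp(βxⱼ + γₖ),

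where j runs over patients at risk in trial k only. The factor exp(γₖ) is common to numerator and denominator and cancels, leaving exp(βxᵢ) / Σⱼ exp(βxⱼ), which is the reduced model. So LR = 0 on 0 df, and γₖ has no estimate, standard error or p-value. No assumed rate enters this result.

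**3. Numerical confirmation.** Data were simulated for six trials at the accrual goals: 1:1 allocation, exponential DFS with 72% at 3 years, censoring uniform on 1.5 to 6 years.

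- In one data set with trial HRs 0.8, 1.0, 1.3, 1.0, 1.5 and 0.9 (4,568 events), the log partial likelihood was −33687.278 with the dummy coefficients at 0, 1, −3 or 10. The information for the dummies was 0.
- On the same data, the test with treatment-by-trial terms gave LR = 37.0 on 5 df, p = 5.9 × 10⁻⁷.
- Rejection rates over 200 replicates per scenario, each test referred to chi-square on 5 df:

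| Scenario | As written | Stratified, treatment-by-trial terms | Unstratified, trial dummies |
|---|---|---|---|
| Common HR, equal baselines | 0% | 4% | 7.5% |
| HRs 0.85, 1.0, 1.2, 1.0, 1.3, 0.9 | 0% | 94% | 94% |
| Common HR, baselines differ by trial | 0% | 3% | 100% |

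In the third row the baseline hazards were multiplied by 1, 0.8, 0.9, 1, 1.2 and 0.7 (assumed). It shows why dropping the stratification is no repair: that test responds to differences in prognosis between trials. With HR 1.0 everywhere, 3-year DFS of 72% in half the trials and 76% in the rest made it reject in 99.5% of 200 replicates; 72% against 74% gave 48%. These baseline contrasts are illustrative, since the documents do not give trial-specific rates.

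**4. What the corrected test could detect.** Assume 3,390 events split in proportion to the accrual goals: 579, 1085, 616, 493, 247 and 370. With SE = 2/√events per trial, the non-centrality is Σ(eventsₖ/4)(log HRₖ − pooled log HR)², and the 5 df critical value is 11.07.

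- TOSCA and SCOT hold (2350 + 4400)/13,750 = 0.491 of the events. With HR 0.90 there and 1.20 in the other four, pooled log HR = 0.491 × (−0.105) + 0.509 × 0.182 = 0.041, so HR = 1.04. Non-centrality = 847.5 × 0.491 × 0.509 × 0.288² = 17.5; power 92%.
- HR 0.95 against 1.15: non-centrality 7.7; power 55%.
- Trial log HRs drawn from a normal distribution with SD 0.05, 0.10, 0.15 or 0.20: average power 14%, 45%, 73% or 88%.

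**The case against.** The best defence is that the intention is plain. The section is about treatment-effect heterogeneity, and it goes on to read out trial-specific hazard ratios, which exist only if the indicators multiply treatment. On that view the text is loose notation. The error would also show itself: software would report coefficients that cannot be estimated, so the literal model could not raise a false alarm. Trial HRs with confidence intervals are planned at both looks, and the cited Section 4.2.2 may hold a second procedure. Section 5.2 names hypotheses, error rates and event numbers as parallel for OS, but not heterogeneity testing. Finally, IDEA is a secondary objective of this trial, and the celecoxib analysis is untouched.

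Much of this limits the reach of the point. Interaction terms probably were meant. It cannot be said that no other formal check exists, only that the primary one is unusable as written. The carry-over to OS is a reasonable reading of Section 5.2, not an explicit statement. The 0.90/1.20 pattern shows what is arithmetically possible; the plan itself expects no superiority for shorter treatment.

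The defect itself stands. The product terms are not written, and an analyst who finds the dummies dropped must choose a replacement with the data in hand. One obvious choice, removing the stratification, gives a test of the wrong thing.

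**Conclusion.** The concern holds. As specified, the primary heterogeneity test in Appendix VI, Section 4.2.1 returns LR = 0 on 0 df for every possible data set, and its follow-up p-values are not estimable. This is an algebraic result and rests on no assumption. The power figures for the corrected test do rest on assumptions: the proportional event split, the 2/√events standard error and the chosen HR patterns.

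The consequence is moderate. The pooled HR, its critical values and the 90% power are unaffected, and the forest plot can still show differences descriptively. What fails is the primary formal rule for declaring that the duration effect varies between trials. This should be fixed; it does not threaten the pooled estimate.

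**What to change.** In Section 4.2.1, keep both models stratified by trial. Define the full model as treatment plus treatment-by-trial interaction terms (5 df for six trials) and the reduced model as treatment only. Apply the likelihood ratio test at p < 0.05 and read the trial-specific HRs from the interaction model. Cochran's Q on the trial log HRs would be an equivalent alternative.

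Also supply Section 4.2.2 or remove the reference to it.

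The cost is one sentence and a cross-reference, with no new data and the same software. For DFS, Section 13.1 of the protocol already cites a reported IDEA result, so the action is to confirm which heterogeneity model was fitted and to rerun the test if it was not the interaction model. For OS, write the corrected test into the formal analysis plan that Appendix VI, Section 5.0 says is still to be developed.
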